Because LA may increase the risk of hypoglycemia in diabetics, otherwise eligible subjects who are diabetics must have their diabetes controlled on non-insulin medications. Safety monitoring labs at every visit for all subjects includes non-fasting blood glucose levels, and HbA1c levels.

Because the risks of LA taken with DMTs are unknown, safety laboratory monitoring will screen for interactions affecting target organs. Subjects will be advised not to drink alcohol while taking the investigational drug and to store it out of reach of children.

The risk of falls during gait testing will be minimized by having trained research staff present at all times during gait testing, and a gait belt will be utilized as needed. Gait testing will be aborted if there is concern for safety or falls by either the participant or research staff.

Risks of MRI will be minimized by careful attention to MRI exclusion criteria at the screening visit including those who require non-oral sedatives during the scan. Any incidental findings unrelated to the study found on MRI such as brain tumors, stroke, etc., will be reviewed by the site treating neurologist who will consider referral to the appropriate medical service, determine ongoing safety for the subject's continued participation in the study, and to fulfil any reporting requirements necessary. Site treating neurologists will counsel subjects with unexpected findings on MRI to minimize any psychological trauma incurred by the discovery.

Overall, the risks of LA are considered minimal and are outweighed by the potential benefits to be gained by the study.

5.1n. Data banking: MRI and images and analyses results along with subject demographics and medical histories will be banked in the VAPORHCS Biorepository for Neurological Diseases (BND #2916). The only PHI included in the data repository is the date of study visit. These dates are necessary for the proper identification of images and data in subjects with multiple data entry points. The banking of the images is described in the Informed Consent Form (ICF).

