5.5f. Inclusion/Exclusion review: Eligibility criteria are reviewed by the treating neurologist during the screening visit. Once all criteria are met and confirmed at the baseline visit, the study staff will use REDCap to assign a randomization code and then

request study drug using the blinded randomization code. For logistical purposes, this may occur prior to M0 visit day to avoid excessive M0 study visit times. Each site pharmacy will then dispense the drug according to the assigned treatment on the randomization schedule, which will be located at each site pharmacy. Subject screens who do not meet inclusion/exclusion requirements will be accounted for in the recruitment monitoring process (See 5.2 Recruitment Methods).

5.5g. Walking tests. The T25FW and 2MTW will be collected at the screening and baseline visits, and every 6 months during the study (21, 22). For the T25FW, subjects are instructed to walk 25 feet marked on the ground "quickly but safely" (Appendix F). The measure is immediately repeated and the two results averaged. Assistive walking devices including canes and walkers are permitted. The 2MTW determines the distance a participant walks in 2 minutes. Dalfampridine is an FDA-approved symptomatic treatment for improving walking speed in MS. Subjects will be asked to maintain their usual dose of dalfampridine at all study visits. Subjects will be strongly encouraged to use the same assistive devices (insoles, orthotics, canes, walkers, etc.) if used at the study start throughout the remainder of the study as safely possible. Subjects who become unable to complete the mobility testing during the course of the study due to worsening MS will continue the study and be analyzed as having worsening mobility according to the data analysis plan. Subjects who are unable to complete mobility testing for non-MS related reasons will not have data recorded for that study visit. Because gait testing is the primary outcome measure, subjects should be tested as early as possible during each study visit. Testing conditions should be as uniform as possible from visit to visit (see 5.1 Study Design, Study timeline and visit scheduling).

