5.5h. EDSS: The EDSS is an eight functional system scale to assess overall MS disability including motor, sensory, cerebellar, brain stem, visual, mental, sphincteric, and other systems (24). Each functional system is graded from 0 (no disability) to 5 or 6 (maximal disability). An integrated score between 0 (normal examination) and 10 (death from MS) is formed based on the score in each functional system. The EDSS exam will be performed by a blinded and trained EDSS examiner who is not the subject's usual treating neurologist (Appendix G).

5.5i. 9HPT: The 9 Hole Peg Test (9HPT) is a timed test of upper extremity arm and hand function. Subjects place pegs into a platform with hole and then take them out again (Appendix F). The 9HPT and T25FW will be administered in accordance with the instructions for the Multiple Sclerosis Functional Composite (21).

5.5j. Cognitive tests: Cognitive testing will utilize the Brief International Cognitive Assessment for MS (BICAMS (25) which includes the Symbol Digit Modalities Test (26) (Appendix H), the California Verbal Learning Test- Second Edition (27) (Appendix I),

and the Brief Visuospatial Memory Test- Revised (28) (Appendix J). These measures will be assessed at baseline, M12 and M24.

5.5k. Patient-reported outcome measures: The Patient Reported Outcome Measures Information Systems (PROMIS) will pain intensity (Appendix K), pain interference (Appendix L), and ability to participate in social roles (Appendix M) (29). Additional measures of depression (Patient Health Questionnaire-9, Appendix N), sleep the previous 4 weeks (Sleep Scale from the Medical Outcomes Study, Appendix O), exercise (Godin Leisure-Time Exercise Questionnaire, modified, Appendix V), and the Modified Fatigue impact Scale (Appendix P) will be administered at baseline and every 6 months thereafter (30, 31). The Fall Efficacy Scale-International (FESI) (Appendix T) is administered annually.

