Subjects will be encouraged to remain in the study through study completion if they start, stop, or switch a DMT, if their disability progresses due to MS to an EDSS of more than 6.5, or if they have an MS relapse. Subjects who develop MRI contraindications may continue through the study end without further MRIs. Study staff will review eligibility at study visits and during regularly scheduled meetings.

5.5p. Investigational drug dispensing: Drug dispensing occurs at baseline and every study visit according to dispensing schedules by the site research pharmacies.

5.5q. Subject/provider blinding questionnaire: All blinded study staff and subjects take a blinding questionnaire at M24 to evaluate the blind (Appendix S).

5.5r. Subject disposition form: Final disposition of each subject is recorded on this form at the M24, early termination visit, or when determined that the subject is unable to attend an early termination visit.

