5.6 Data Analysis

5.6a. Sample size: The sample size and power analysis were based on the pilot LA in SPMS trial in which LA had improved time to complete the T25FW (-0.54 seconds SD 0.36 vs 0.14 SD 0.25, p = 0.06). A sample size of 44 per group will have 80% power to detect a difference between the LA group with a coefficient, β_1 regression slope of -0.50 seconds and the placebo group coefficient, β_2 slope of -1.00, assuming that the standard deviation of the difference between the groups is 2.20 and the standard deviation of the residuals (repeated measures within each participant) is 1.80 with a 0.05 two-sided significance level and the correlation of 0.85 between the measurements over time, which if lower increases the power. The delta of improvement is a reduction in the rate of walking slowing of 0.5 seconds per unit of time. This translates into 2 seconds on the average timed walk over 2 years. A sample size of 59 per arm will allow for a 25% drop-out rate. The pilot study had a 10% drop out rate however 25% is more realistic for a multi-site trial in an era with more therapeutic options for MS. Screen visit failures are likely to be minimal (<10% of all screen visits) as most eligibility requirements can be made prior to the screening visit using the methods described in 5.2 Recruitment Methods.

As a check on these calculations we compared the estimates, Altmann et al.'s estimates of sample size when using SIENA as the method of determining whole brain atrophy rate, the current sample of 44 per group will achieve 80% power at significance level 0.05 assuming a 40-50% effect size (33).

5.6b. Data analysis plan: Data is analyzed by the SCC at study completion or at any point requested by the DSMB. Only subjects that complete the baseline evaluation and take at least one dose of study drug will be included in the data analysis.

The SCC will use the mixed model approach to compare, between the treatment groups, mean rates of change from baseline in the times to complete the T25FW. The SCC will use the transformation 25/T25FW, which is the walking speed in feet per

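### Section 5.5g promises that MS-related inability to walk will be analysed as worsening, but 5.6b contains no rule that does so, and its gait-worsening definition runs in the wrong direction

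*Combined protocol and SAP*

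**What the plan says.** Section 5.5g treats two kinds of uncompleted walk differently. Subjects who lose the ability because of worsening MS "will continue the study and be analyzed as having worsening mobility according to the data analysis plan". For the other kind: "Subjects who are unable to complete mobility testing for non-MS related reasons will not have data recorded for that study visit". So the rule for the first kind is to be found in 5.6b.

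Section 5.6b contains the following:
- **Primary analysis:** a mixed model comparing rates of change in walking speed, computed as 25 divided by the T25FW time, with baseline disability as a predictor.
- **Secondary gait-worsening proportion:** a 20% threshold on T25FW and/or 2MTW, and/or a need for more walking assistance. The threshold is worded as an improvement.
- **Exploratory composite:** sustained EDSS change, the same gait-worsening definition, or a 20% rise in 9HPT.
- **Missing data:** mentioned only in the falls paragraph.
- **Sensitivity analysis:** the one that is named concerns change of disease-modifying therapy.

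Such visits are foreseeable. Entry is allowed up to EDSS 6.5 with recent progression (5.4), and 5.5o encourages subjects to stay in the study "if their disability progresses due to MS to an EDSS of more than 6.5".

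**The concern.** The trial asks whether LA maintains mobility, and losing the walk is the plainest failure to maintain it. Section 5.5g recognises this and defers to a rule that 5.6b does not contain. Three consequences follow.

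- A subject who stops walking because of MS has no T25FW time, hence no speed. A likelihood mixed model then uses only the earlier visits. The distinction drawn in 5.5g has no effect on the primary result.
- The gait-worsening endpoint, and the composite that borrows it, count such a subject only by interpretation, for example if a 2MTW distance of 0 is entered or if inability is read as needing more assistance.
- Programmed literally, the T25FW and 2MTW parts of that endpoint would count subjects who got better.

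If the rule is left open, it could also be chosen after the data are seen, and the choice can move the primary test.

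**Working it through.** **1. Rule against method**

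| Case | 5.5g | 5.6b, 25/T25FW model | 5.6b, gait-worsening endpoint |
|---|---|---|---|
| MS-related inability | analyse as worsening | no value assigned | not named |
| Non-MS inability | no data for the visit | no value assigned | not named |

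The two rows differ in 5.5g and are identical in 5.6b.

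**2. The plan's own effect.** Section 5.6a gives slopes of 0.50 s (LA) and 1.00 s (placebo) per unit of time, read here as slowing. It says of the 0.5 s difference: "This translates into 2 seconds on the average timed walk over 2 years". Then 2 / 0.5 = 4 units in 2 years, so one unit is 6 months. LA slows by 4 × 0.50 = 2 s and placebo by 4 × 1.00 = 4 s. The stated 2 s reproduces.

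**3. On the speed scale.** Speed at 2 years = 25 / (25/s0 + slowing). Baseline speed s0 is assumed, because the documents give none.
- s0 = 3.3 ft/s: LA 25/9.58 = 2.61, placebo 25/11.58 = 2.16. Falls are 0.69 and 1.14; effect 0.45 ft/s.
- s0 = 4.5 ft/s: LA 25/7.56 = 3.31, placebo 25/9.56 = 2.62. Falls are 1.19 and 1.88; effect 0.69 ft/s.

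**4. Hand check at M24.** Suppose loss is abrupt, is complete by M24 and is unrelated to speed. Omission then leaves the effect at 0.45 (s0 = 3.3). Scoring 0 multiplies each arm's mean by the share still walking.
- 10% placebo, 5% LA: 0.95 × 2.61 − 0.90 × 2.16 = 0.54. Ratio 0.45/0.54, about 84%.
- 5% placebo, 10% LA: 0.90 × 2.61 − 0.95 × 2.16 = 0.30. Ratio about 1.5.
- Equal 10%: 0.90 × 0.45 = 0.41. Ratio about 1.11.

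**5. Simulation of the longitudinal model.** A random intercept and slope model with visits at M0, 6, 12, 18 and 24 was fitted twice, with inability visits omitted or set to 0. Assumed inputs: loss at a visit uniform over M6-M24, and the slower half three times as likely to lose the walk. Slowing follows 5.6a, either in seconds (slope SD 0.5 or 1.0 s per 6 months, residual 8%) or as falls of the same size that are linear in speed.

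| Loss | Omission as share of speed-0 estimate |
|---|---|
| Gradual (seconds scale) | 98-100% |
| Abrupt, equal 5% or 10% (seconds scale) | 104-114% |
| Abrupt, 10% placebo vs 5% LA (both scales) | about 86-93% |
| Abrupt, 5% placebo vs 10% LA (both scales) | about 130-142% |

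For the last row on the seconds scale, the estimates are 0.57 against 0.42 and 0.84 against 0.64 ft/s; 0.57/0.42 = 1.36 and 0.84/0.64 = 1.31. The contrast is milder than in step 4 mainly because loss falls more often on slow subjects, for whom a zero is a smaller drop.

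**6. Power cost of scoring.** Take 44 per arm, tuned to 78% rejection without loss. Omission stays near 76-78% whichever arm loses the walk more often. With falls of the size in step 3, scoring 0 gives 46-54% for equal 10% loss and about 37% for 5% placebo vs 10% LA. With smaller falls (placebo losing 0.30 ft/s in 2 years), equal 10% loss gives 38-43% for zeros and 59-61% for a worst-rank test.

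**The case against.** **Section 5.5g may not be aimed at the primary model.** It speaks of worsening mobility, and the only worsening category in 5.6b is the secondary gait endpoint. This is a fair reading and cannot be excluded. It does not close the gap: that endpoint does not name inability and its threshold points the wrong way.

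**Section 5.6b never says to omit these visits.** Correct. A reader might infer that the plan instructs omission, but the documents leave the method unstated. Omission is what mixed-model software does by default.

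**The coding rule may exist elsewhere.** Section 5.5i says "The 9HPT and T25FW will be administered in accordance with the instructions for the Multiple Sclerosis Functional Composite", and Appendix F and the Manual of Operations could also carry a rule. None of these was available. Section 5.5g, however, sends the reader to the data analysis plan, which cites none of them. How to treat a walk stopped for safety (5.1m), or one failed attempt of the two that are averaged, is scoring detail that may be settled there, and the point does not depend on it.

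**The harm is conditional and a remedy has a price.** This stands. The loss rates, speeds and loss patterns are all assumed, and gradual loss, the more natural course under the entry criteria, changes almost nothing. Treating speed 0 as the reference is itself a choice of estimand. The simulated model also leaves out the baseline-disability predictor. A reader might infer that the primary result would be badly biased, or that 0 ft/s must become the primary rule. Neither follows.

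**Conclusion.** The textual gap is firm: 5.5g defers to a rule that 5.6b does not state, and the gait-worsening definition has the wrong direction as written. The direction error is almost certainly a slip, but it sits in an operative endpoint definition and carries into the composite. The composite's EDSS component may still catch some of these subjects.

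The effect on the primary estimate is uncertain. It is material only if loss of walking is abrupt and unequal between arms, and no scenario at the planned effect reversed its sign. The percentages rest on assumed loss rates of 5% and 10%, assumed baseline speeds of 3.3 and 4.5 ft/s, and slowing as planned in 5.6a. They show that the choice of rule can matter, and they do not predict what the trial will find. This should be fixed, and it does not put the design in doubt.

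**What to change.** Amend 5.6b before unblinding:

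1. Restate the gait threshold as 20% worsening, meaning a longer T25FW time or a shorter 2MTW distance.
2. Count MS-related inability explicitly as worsening in the gait-worsening endpoint and in the composite.
3. State how MS-related inability enters the T25FW analysis. At minimum, prespecify one analysis that scores it as 0 ft/s or worst rank, next to the mixed model that leaves it missing. Keep non-MS inability missing, and report inability visits by arm and reason.
4. If Appendix F, the MSFC instructions or the Manual of Operations already set a rule, cite it.

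Which version is primary is for the sponsor to decide and name in advance, because scoring inability costs power when loss is equally common in both arms (step 6 of the working).

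The change is a few sentences of analysis text, plus a check that the case report form records why a walk was not completed. Section 5.5g implies that the reasons are separated, but no section describes the field. No visit, procedure or sample size changes.

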5.6 Data Analysis

5.6a. Sample size: The sample size and power analysis were based on the pilot LA in SPMS trial in which LA had improved time to complete the T25FW (-0.54 seconds SD 0.36 vs 0.14 SD 0.25, p = 0.06). A sample size of 44 per group will have 80% power to detect a difference between the LA group with a coefficient, β_1 regression slope of -0.50 seconds and the placebo group coefficient, β_2 slope of -1.00, assuming that the standard deviation of the difference between the groups is 2.20 and the standard deviation of the residuals (repeated measures within each participant) is 1.80 with a 0.05 two-sided significance level and the correlation of 0.85 between the measurements over time, which if lower increases the power. The delta of improvement is a reduction in the rate of walking slowing of 0.5 seconds per unit of time. This translates into 2 seconds on the average timed walk over 2 years. A sample size of 59 per arm will allow for a 25% drop-out rate. The pilot study had a 10% drop out rate however 25% is more realistic for a multi-site trial in an era with more therapeutic options for MS. Screen visit failures are likely to be minimal (<10% of all screen visits) as most eligibility requirements can be made prior to the screening visit using the methods described in 5.2 Recruitment Methods.

As a check on these calculations we compared the estimates, Altmann et al.'s estimates of sample size when using SIENA as the method of determining whole brain atrophy rate, the current sample of 44 per group will achieve 80% power at significance level 0.05 assuming a 40-50% effect size (33).

5.6b. Data analysis plan: Data is analyzed by the SCC at study completion or at any point requested by the DSMB. Only subjects that complete the baseline evaluation and take at least one dose of study drug will be included in the data analysis.

The SCC will use the mixed model approach to compare, between the treatment groups, mean rates of change from baseline in the times to complete the T25FW. The SCC will use the transformation 25/T25FW, which is the walking speed in feet per

Adverse and serious adverse events will be tabulated and compare the differences in the occurrence and the frequencies between the two groups. The frequency of side effects will be compared using χ^2 tests or Fisher's exact test as appropriate depending on the number of adverse events seen. For evaluation of patient safety, laboratory test results at baseline and changes from baseline will be summarized and compared using t-tests for continuous measures and Fisher's exact test for proportions.

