5.0 Study Procedures

5.1 Study Design

5.1a. Design and specific aims: This is a phase 2, double-blind, multi-center RCT to compare the daily administration of 1200 mg oral LA to a placebo, as a disease-modifying treatment in PMS. A total of 118 subjects with PMS will be randomized 1:1 to LA or placebo. None of the study procedures involve usual care. All study procedures will be covered by study funding.

5.1b. Study population: A convenience sample of adults with PMS will be recruited from the study sites. The multi-site design of the trial is intended to promote generalizability of the study results.

5.1c. Study timeline and visit scheduling. The anticipated study recruitment period is for the first 18 months once the study is approved at the first study site or until enrolment is completed, whichever occurs first. The study will end when the last participant exits the study. There should be no more than 60 days inclusive between the screen and baseline visits. Subsequent study visits will occur at 3 months, 6 months, and every 6 months thereafter, each visit within +/- 2 weeks from the ideal visit based on the baseline/month zero (M0) visit. The MRI can take place up to 2 weeks prior to the baseline and final visits. Should the final MRI be postponed for any reason until after the

final visit, the subjects should continue taking study drug until the MRI has been done. Reasons for conducting visits outside the scheduling window are recorded.

Performance on clinical measures may be subject to variation due to the day-to-day fluctuations characteristic of PMS. Effects of fluctuations on study outcomes will be minimized by encouraging subjects to maintain their usual sleep, eating, and medication intake patterns on study days. Study visits will be scheduled at the same time-period each visit (morning versus afternoon). Study visits may be postponed for concurrent non-MS related illness affecting neurological performance on the discretion of the treating neurologist.

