5.5b. Consent, medical history, general medical exam: The ICF will be presented by the PI, LSI, or designated study staff. After consent has been obtained, the rest of the study procedures can occur. The medical history and general medical exam is conducted by the treating neurologist for the purpose of eligibility.

5.5c. Vital signs: Resting blood pressure, pulse, and weight are collected by trained study staff at every study visit for the purpose of initial eligibility and ongoing health monitoring. Consistent methods of obtaining data (e.g. same resting period prior to blood pressure and pulse assessments, etc.) is encouraged across study visits. Height is assessed at the screening visit only.

5.5d. Concomitant medication review: Current use of prescribed scheduled and as needed medications as well as over the counter medications and supplements is recorded by the study staff and reviewed at the screen visit by the treating neurologist for study eligibility. Concomitant medications are reviewed at each subsequent visit by study staff and changes reviewed by the treating neurologist. Any start, stop, or change to MS disease-modifying therapies will be noted and dated for data analysis purposes. Supplements will be reviewed by research staff in case they contain lipoic acid or other potential confounders to the study results.

5.5e. Safety laboratory analyses: Laboratory studies will be collected from all subjects at the screening visit if not available within the prior 3 months for establishing eligibility. Additional laboratory analyses occur at visits M3, M6, M12, M18 and M24 to monitor blood cell count, renal function, liver function, urine protein, non-fasting blood glucose levels, HbA1c, and (for women of child-bearing potential) pregnancy testing. Subjects must have urine protein monitored every 3 months for the duration of the study. Pregnancy testing is additionally conducted at the baseline visit for women of child-bearing potential. This involves taking approximately 15-25 mL (3 to 5 teaspoons) of blood at each draw for a total of 90-150mL (2/3 cup) over the course of the study. Laboratory draws will be performed by trained phlebotomists using universal precautions.

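### Continuous laboratory changes are compared by t-test without baseline adjustment or use of the repeated visits; a baseline-adjusted model would be somewhat more precise at no cost

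*Combined protocol and SAP*

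**What the plan says.** The last paragraph of section 5.6b covers laboratory safety: "laboratory test results at baseline and changes from baseline will be summarized and compared using t-tests for continuous measures", with "Fisher's exact test for proportions". It mentions no covariate, no visit, no handling of repeated or missing values and no interval estimate.

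Section 5.5e sets the collection schedule: "Additional laboratory analyses occur at visits M3, M6, M12, M18 and M24". The pre-treatment value comes from screening, or from results already available within the preceding 3 months. The flowsheet in 5.5a shows only a pregnancy test at M0, so laboratory baseline means this earlier value.

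Elsewhere in 5.6b the plan uses mixed models for the T25FW, falls and SIENA. For falls it gives within-subject correlation and missing data as the reasons.

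**The concern.** Renal and liver effects are prominent safety questions here. Section 2.0 attributes a biopsy-proven glomerulonephritis and a second proteinuria case in the pilot to lipoic acid. Section 5.1l lists liver, renal and urinary disorders as risks, and 5.1m sets out detailed monitoring. The continuous comparison is where a shift in mean eGFR or transaminases below the event thresholds would show, so its precision has some value.

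The stated method falls short in three ways:

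- A change score subtracts baseline with its coefficient fixed at 1. Estimating the coefficient is more efficient whenever the correlation is below 1. It also deals properly with a chance baseline difference d, which shifts the change-score contrast by -(1 - rho) × d.
- Laboratory values are taken at five post-baseline visits with a planned 25% dropout, yet they get a plain t-test with no visit named.
- Baseline values are compared between arms. They precede randomisation, so any difference between the randomised arms is chance and a test of it answers no question.

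**Working it through.** **What the plan offers to reproduce.** There is no SD, correlation or power figure for any laboratory comparison. The only sample size is for the T25FW: 44 per group, and 44/0.75 = 58.7, rounded up to 59 per arm (5.6a). That reproduces the 118 randomised but says nothing about laboratory precision. The 0.85 correlation in 5.6a is also for the T25FW.

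**Inputs.** n = 59 per arm (5.1a, 5.6a). The correlation rho between the pre-treatment and follow-up laboratory value is an assumption, shown from 0.5 to 0.95. The SD sigma is taken as equal at both times and in both arms.

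**Formulas, single visit.**

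- Change score: variance per subject = 2 × sigma² × (1 - rho)
- ANCOVA: variance per subject = sigma² × (1 - rho²)
- Ratio ANCOVA/change = (1 - rho²) / [2(1 - rho)] = (1 + rho)/2
- Detectable difference in SD units at 80% power, two-sided 0.05: (1.960 + 0.842) × sqrt(2 × variance / 59)

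Example at rho 0.7: change-score variance 2 × 0.3 = 0.60; ANCOVA variance 1 - 0.49 = 0.51; ratio 0.51/0.60 = 0.85. The t-test standard error is larger by sqrt(1/0.85) - 1 = 8.5%.

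| Assumed rho | Variance ratio | t-test SE larger by | Detectable difference, t-test vs ANCOVA (SD) | ANCOVA power where t-test has 80% |
|---|---|---|---|---|
| 0.5 | 0.75 | 15.5% | 0.516 vs 0.447 | 89.9% |
| 0.7 | 0.85 | 8.5% | 0.400 vs 0.368 | 86.0% |
| 0.85 | 0.925 | 4.0% | 0.283 vs 0.272 | 83.0% |
| 0.95 | 0.975 | 1.3% | 0.163 vs 0.161 | 81.0% |

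**Check by simulation.** With 59 per arm and 20,000 runs per rho, the variance ratios were 0.745, 0.862 and 0.932 at rho 0.5, 0.7 and 0.85, against 0.75, 0.85 and 0.925 from the formula. Both estimators averaged about zero when there was no true difference, so neither is biased.

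**How much baseline information the change score keeps.** Using follow-up values alone would have variance 1/[2(1 - rho)] relative to the change score: 1.00 at rho 0.5, 1.67 at 0.7 and 3.33 at 0.85. When rho is well above 0.5 the change score has already captured much of the benefit.

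**Which analytes suit the model.** The routine list in 5.5e covers renal and liver function for everyone, so eGFR, ALT and AST have a pre-treatment value and scheduled repeats. ACR differs. Under 5.1m it is measured only after urine protein of 1+ or higher, at screening and on study. Most subjects may have no pre-treatment ACR, and on-study ACR exists only in a subset selected by a post-randomisation result. An arm comparison of mean ACR in that subset would not be a randomised comparison.

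**The case against.** The strongest reply is that nothing here is invalid. The change-score t-test is unbiased under randomisation, no laboratory comparison is powered, and if laboratory values correlate at 0.85 to 0.95 the standard-error penalty is only about 1% to 4%. The documented renal risk is proteinuria and glomerulonephritis, which are events. The plan handles these through the ACR and eGFR thresholds and the check on a 25% eGFR fall (5.1m), liver grading by CTCAE, mandatory REDCap reporting of specified renal and liver findings (6.3a), quarterly DSMB reports by arm (6.8) and Fisher's exact test. A model for means changes none of that. All of this stands, and it is why the point is minor.

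Three stronger readings are tempting, and the documents do not support them:

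- *The plan discards the baseline value.* It does not. Baseline is subtracted in the change score and is also summarised. What is missing is adjustment with an estimated coefficient.
- *The plan runs a separate t-test at each visit.* The text names no visit. The gap is that the visit and the use of the repeated measures are unspecified.
- *Renal and liver safety conclusions are compromised.* Only the comparison of continuous means loses precision.

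The reply does not show that the t-test is preferable. The adjustment uses data already collected and a type of model that the plan already applies to other outcomes.

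**Conclusion.** The point holds as a free improvement of minor weight. The stated analysis is valid but less precise than a baseline-adjusted one. At a single visit the gain is a variance 25% smaller at rho 0.5, 15% at 0.7, 7.5% at 0.85 and 2.5% at 0.95. This assumes equal SDs over time and between arms, and the size for eGFR, ALT or AST cannot be fixed from the protocol. Any further gain from pooling the five visits, or from including site, was not computed and is not claimed. A repeated-measures model would also settle which comparison is made, which the present sentence leaves open. The baseline tests bias nothing but are uninformative.

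**What to change.** Replace the laboratory sentence in 5.6b with wording such as: *Values of eGFR, and of ALT and AST on the log scale, at M3, M6, M12, M18 and M24 will be analysed in a repeated-measures mixed model with the screening (pre-treatment) value, arm, visit, arm-by-visit interaction and site. Differences between arms will be reported by visit with 95% confidence intervals. Baseline values will be summarised by arm without significance tests.* Site belongs in the model because randomisation is blocked by site (5.1j).

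Keep ACR out of this model. Report it as a proportion, for example new ACR above 300 mg/g as already captured under 6.3a, compared by Fisher's exact test. State that the denominator is all analysed subjects in the arm, and that those never triggering an ACR measurement count as without the event. Leave the other proportion, threshold and grade summaries as they are.

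The cost is SAP wording and a little programming. No new data, visits or subjects are needed.
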